- Protocol Appendix E, Activity Schedule: Updated the Activity Schedule (Appendix E) to reflect changes in the study design and to include additional activities for specific visits. Updated abbreviations list at end of table.

Rationale: *To reflect all the changes in activities scheduled on specific visits and additional abbreviations.*

- Operations Manual, Section 1 Contacts: Updated the name of the Certified Clinical Lab to Labcorp Central Laboratory and updated the name and contact of the Biomarker Sample storage from Brooks Life Sciences Brooks Receiving to Azenta Life Sciences.

Rationale: *The name of the certified clinical lab changed from Covance Central Laboratory to Labcorp Central Laboratory and the name of the biomarker sample storage changed to Azenta Life Sciences.*

- Operations Manual, Section 2.1 Individual Treatment Period Visits Activities; Section 2.2 Post-Treatment Activities: Added an extra column/dot to the column headers of the Individual Study Day tables.

Rationale: *To reflect the addition of the 30-day post-treatment follow-up phone call.*

- Operations Manual, Section 2.1 Individual Treatment Period Visits Activities: Deleted subsequent instances of full terms for high-sensitivity C-reactive protein and Health Assessment Questionnaire Disability Index since already defined at first use and acronym provided.

Rationale: *To remove redundancy.*

- Operations Manual, Section 2.1 Individual Treatment Period Visits Activities: Added "Rheumatoid Factor" for Week 78 visit.

Rationale: *Added to align with Activity Schedule (Appendix E).*

- Operations Manual, Section 2.1 Individual Treatment Period Visit Activities: Added a 7-day treatment period window for the LTE Period 2, starting at Week 86.

Rationale: *To inform that a longer treatment window period of 7 days will be allowed for the LTE Period 2. This will give flexibility to the subjects that opted for dosing at home and will maintain the 7-day treatment window considered safe between doses.*

- Operations Manual, Section 2.1 Individual Treatment Period Visits Activities: Corrected the spelling of "virtual."

Rationale: *To correct the typographical error.*
- Operations Manual, Section 2.1: Updated study visit day tables and individual visit activities for LTE Period 1, LTE Period 2, 30-Day Follow-Up Phone Call, Week 182 Final Study Visit, and 70-day Follow-up Visit.

Rationale: *To reflect updated schedule of activities as described in the Activity Schedule ([Appendix E](#)).*
- Operations Manual, Section 2.1 Individual Treatment Period Visits Activities: Corrected the AE assessment during the Screening Period to only study procedure-related SAEs and non-serious AEs.

Rationale: *To align with the Operations Manual Section 4.1 Methods and Timing of Safety Assessment.*
- Operations Manual, Section 2.1 Individual Treatment Period Visits Activities Week 26, 28, 32, 34, 38, 40, 44, 46, 50, 52, 56, 58, 62, 64, 68, 70, 74, 76: Added supervised training for study drug administration at home at Week 76 and corresponding footnote "a" to inform that if administration of study drug at home is not locally permitted or not opted by the subject, training for home administration is not required.

Rationale: *To ensure proper training for subjects which will be dosing at home during LTE Period 2 and clarify that if administration of study drug at home is not locally permitted or not opted by the subject, training for home administration is not relevant.*
- Operations Manual, Section 2.1 Individual Treatment Period Visits Activities, Week 4 (Day 29), Week 8 (Day 57), Week 12 (Day 85), Week 18 (Day 127), Week 24 (Day 169), Week 30, 36, 42, 48, 54, 60, 66, 72, 78, 86, 94, 102, 110, 118, 126, 134, 142, 150, 158, 166, 174, Week 182 (Final Study Visit), Premature Discontinuation: Removed definition of ADA (anti-drug antibody) and nAb (neutralizing antibodies) abbreviations.

Rationale: *Definition of ADA and nAb abbreviations were provided on Week 2 (Day 15).*
- Operations Manual, Section 2.1 Individual Treatment Period Visits Activities Weeks 30, 36, 42, 48, 54, 60, 66, 72, 78, 86, 94, 102, 110, 118, 126, 134, 142, 150, 158, 166, 174: Added the TB risk questionnaire, QuantiFERon-Tb Gold test (and/or local PPD Skin Test), and Chest X-ray to Weeks 110 and 166.

Rationale: *To ensure subject safety through annual TB assessments during administration of study drug.*
- Operations Manual, Section 2.1 Individual Treatment Period Visits Activities Weeks 30, 36, 42, 48, 54, 60, 66, 72, 78, 86, 94, 102, 110, 118, 126, 134, 142, 150, 158, 166, 174: Updated PGIC – FLARE to Week 78 only.

Rationale: *To align with the activity schedule Appendix E for the LTE Period 1 where PGIC – FLARE is performed at Week 78.*
- Operations Manual, Section 2.1 Individual Treatment Period Visits Activities Weeks 30, 36, 42, 48, 54, 60, 66, 72, 78, 86, 94, 102, 110, 118, 126, 134, 142, 150, 158, 166, 174: updated PGIS –

FLARE to Weeks 30, 36, 42, 48, 54, 60, 66, 72, 78, 86, 94, 102, 110, 118, 126, 134, 142, 150, 158, 166, and 174.

Rationale: *To reflect the updated schedule of activities related to the LTE Period 2 as described in the Activity Schedule (Appendix E).*

- Operations Manual, Section 2.1 Individual Treatment Period Visits Activities Weeks 30, 36, 42, 48, 54, 60, 66, 72, 78, 86, 94, 102, 110, 118, 126, 134, 142, 150, 158, 166, 174: Updated the physical exam to Weeks 36, 48, 60, 72, 78, 86, 94, 118, 142, and 166.

Rationale: *To reflect updated schedule of activities related to the LTE Period 2 as described in the Activity Schedule (Appendix E).*

- Operations Manual, Section 2.1 Individual Treatment Period Visits Activities Weeks 30, 36, 42, 48, 54, 60, 66, 72, 78, 86, 94, 102, 110, 118, 126, 134, 142, 150, 158, 166, 174: Updated 12-lead ECG to Weeks 36, 78, and 134.

Rationale: *To reflect the updated schedule of activities related to the LTE Period 2 as described in the Activity Schedule (Appendix E).*

- Operations Manual, Section 2.1 Individual Treatment Period Visits Activities Weeks 30, 36, 42, 48, 54, 60, 66, 72, 78, 86, 94, 102, 110, 118, 126, 134, 142, 150, 158, 166, 174: Updated DXA Scan with body composition to Week 78 and 134. Added footnote "e" to specify the window for obtaining DXA Scan with body composition.

Rationale: *To reflect updated schedule of activities related to the LTE Period 2 as described in the Activity Schedule (Appendix E). To clarify the permitted window for collection of DXA Scan with body composition.*

- Operations Manual, Section 2.1 Individual Treatment Period Visits Activities Week 24 (Day 169), Weeks 30, 36, 42, 48, 54, 60, 66, 72, 78, 86, 94, 102, 110, 118, 126, 134, 142, 150, 158, 166, 174: added "free" to the scheduled biomarker sample of whole blood for cortisol.

Rationale: *To clarify free cortisol is being tested on whole blood.*

- Operations Manual, Section 2.1 Individual Treatment Period Visits Activities Week 24 (Day 169), Weeks 30, 36, 42, 48, 54, 60, 66, 72, 78, 86, 94, 102, 110, 118, 126, 134, 142, 150, 158, 166, 174: added footnote "i" on Biomarker sample: Whole blood for free cortisol, bone markers (BSAP, PINP, OC and CTX), ACTH, and TBNK to inform which visits these biomarker samples are scheduled to be collected.

Rationale: *To reflect updated schedule of activities related to the LTE Period 2 as described in the Activity Schedule (Appendix E).*

- Operations Manual, Section 2.1 Individual Treatment Period Visits Activities Weeks 30, 36, 42, 48, 54, 60, 66, 72, 78, 86, 94, 102, 110, 118, 126, 134, 142, 150, 158, 166, 174: Updated HbA1c to Weeks 36, 48, 60, 72, 94, 118, 142, and 166.

Rationale: *To reflect updated schedule of activities related to the LTE Period 2 as described in the Activity Schedule (Appendix E).*

- Operations Manual, Section 2.1 Individual Treatment Period Visits Activities Weeks 30, 36, 42, 48, 54, 60, 66, 72, 78, 86, 94, 102, 110, 118, 126, 134, 142, 150, 158, 166, 174: updated Lipid profile to Weeks 36, 48, 60, 72, 94, 118, 142, and 166.

Rationale: *To reflect updated schedule of activities related to the LTE Period 2 as described in the Activity Schedule (Appendix E).*

- Operations Manual, Section 2.1 Individual Treatment Period Visits Activities Weeks 30, 36, 42, 48, 54, 60, 66, 72, 78, 86, 94, 102, 110, 118, 126, 134, 142, 150, 158, 166, 174: Revised footnote "a" to describe requirements for urine pregnancy testing both at scheduled visits on-site and at home between visits if time between visits is longer than 1 month. Added timepoints for collection of HbA1c and lipid profile to the table and footnote "a" removed from HbA1c and lipid profile.

Rationale: *To reflect updated schedule of activities related to the LTE Period 1 and 2 that requires urine pregnancy testing during the study at a minimum of monthly intervals and inform which visits the urine pregnancy tests can be collected on-site and which visits the urine pregnancy tests can be collected at home to ensure monthly urine pregnancy testing for females of childbearing potential. Timepoints for collection of HbA1c and lipid profile were added to the table, therefore this information was removed from the footnote.*

- Operations Manual, Section 2.1 Individual Treatment Period Visits Activities Weeks 30, 36, 42, 48, 54, 60, 66, 72, 78, 86, 94, 102, 110, 118, 126, 134, 142, 150, 158, 166, 174: Updated footnote "d" added language to inform that, if necessary, HBV DNA PCR may be tested at unscheduled visits.

Rationale: *To inform that, if necessary, HBV DNA PCR test may be tested at unscheduled visits.*

- Operations Manual, Section 2.1 Individual Treatment Period Visits Activities Weeks 30, 36, 42, 48, 54, 60, 66, 72, 78, 86, 94, 102, 110, 118, 126, 134, 142, 150, 158, 166, 174: Added supervised training for study drug administration at home at Week 78 and corresponding footnote "f" to inform that if administration of study drug at home is not locally permitted or not opted by the subject, training for home administration is not required and that subjects not trained for administration of study drug at home will continue to receive study drug eow in the clinic.

Rationale: *To ensure proper training for subjects which will be dosing at home during LTE Period 2 and clarify that if administration of study drug at home is not locally permitted or not opted by the subject, training for home administration is not relevant and dosing can continue to be performed at the clinic eow after Week 78 (during LTE Period 2).*

- Operations Manual, Section 2.1 Individual Treatment Period Visits Activities Weeks 30, 36, 42, 48, 54, 60, 66, 72, 78, 86, 94, 102, 110, 118, 126, 134, 142, 150, 158, 166, 174: Added Dispensation of study drug for home administration and corresponding footnote "g" to state study drug dispensation for home administration will start at Week 78 and is only applicable where locally permitted or opted by the subject, and that after Week 180 study drug will no longer be dispensed.

Rationale: *To specify start and end of study drug dispensation for home administration and clarify study drug dispensation for home administration is only applicable where locally permitted or opted by the subject.*

- Operations Manual, Section 2.1 Individual Treatment Period Visits Activities Weeks 30, 36, 42, 48, 54, 60, 66, 72, 78, 86, 94, 102, 110, 118, 126, 134, 142, 150, 158, 166, 174: Added Subject

Diary Review and corresponding footnote "h" to inform that subjects who opted for dosing at home will have their diaries reviewed.

Rationale: *To inform that subjects who opted for home dosing during the LTE Period 2 will have their diaries reviewed at specified visits to capture dosing dates and times for dosing compliance.*

- Operations Manual, Section 2.1 Individual Treatment Period Visits Activities Weeks 30, 36, 42, 48, 54, 60, 66, 72, 78, 86, 94, 102, 110, 118, 126, 134, 142, 150, 158, 166, 174: Added footnote "i" to inform the visit schedule for whole blood collection for free cortisol and bone markers.

Rationale: *To align with Activity Schedule (Appendix E).*

- Operations Manual, Section 2.1 Individual Treatment Period Visits Activities Week 182 Final Study Visit: Removed of PGIC – FLARE and bone biomarkers; added HbA1c and lipid profile; added note "a" to inform that subjects who opted for dosing at home will have their diaries reviewed. Changed notes and b to b and c, respectively.

Rationale: *PGIC – FLARE assessment at Week 178 will not be informative since it is based on the patient's recollection of disease activity at baseline and will continue to be collected at the Week 78 visit as previously planned. HbA1c and lipid profile were added to have a robust safety assessment at the updated final study visit at Week 182. To inform that subjects who opted for home dosing during the LTE Period 2 will have their diaries reviewed to capture dosing dates and times for dosing compliance. Footnotes b and updated to align with appropriate activities.*

- Operations Manual, Section 2.1 Individual Treatment Period Visits Activities Week 182 Final Study Visit: Added whole blood biomarker sample for free cortisol.

Rationale: *Whole blood biomarker sample for free cortisol was added to have a robust safety assessment at the updated final study visit at Week 182.*

- Operations Manual, Section 2.2 Post-Treatment Activities: 30-Day Post-treatment Follow-up Phone Call was added, which includes an AE assessment and prior and concomitant medications assessment.

Rationale: *Phone call was added to further ensure subject safety and capture of AEs/SAEs occurring early in the follow up period.*

- Operations Manual, Section 2.2 Post-Treatment Activities Post-Treatment Day 70 Visit: Added body weight, vital signs, whole blood biomarker sample for total and free cortisol, blood samples for serum conjugate ADC (serum), total antibody (serum), free A-1677770 (plasma) assays, and blood samples for serum ADA assays (including nAb), and ADA titer assays to the 70-day follow-up visit.

Rationale: *To ensure more robust safety data collection at follow up. To ensure drug washout and assess immunogenicity during drug washout.*

- Operations Manual, Section 3.2, Re-Screening: Added wording "without prior AbbVie approval" regarding re-screening.

Rationale: *To clarify the re-screening process.*

- Operations Manual, Section 3.5, Dual-Energy X-Ray Absorptiometry (DXA) Scan: Added collection of Z-score for evaluation of bone mineral density and instruction that measurements should be obtained from the distal forearm if neither the spine nor either hip are able to be scanned or interpreted. Added a Central Imaging Core Lab for central independent review of

DXA data and modified guidance for image acquisition. Removed performance of BMD and body composition assessment if DXA scan is not available.

Rationale: *To improve the robustness and interpretability of the DXA data collected. Other methods of BMD and body composition assessment are not interchangeable with DXA.*

- Operations Manual Section 3.15 Subject Dosing Diary: Added Operations Manual Section 3.15 Subject dosing diary to inform when the subjects will be dispensed a diary and the process of diary documentation and review.

Rationale: *To inform subjects who opted for home dosing during LTE Period 2 and where locally permitted when they will receive a dosing diary, how they will be trained and how the dosing diary will be reviewed and properly documented.*

- Operations Manual, Section 3.16 Clinical Laboratory Tests, Table 1. Added Follicle Stimulating Hormone to the table to reflect changes in Protocol Section 5.2.

Rationale: *Follicle Stimulating Hormone testing was added to align with addition of language in protocol section 5.2 which permits re-testing of FSH during study conduct.*

- Operations Manual, Section 3.16 Clinical Laboratory Tests, Pregnancy Tests (Serum and Urine): Updated language to align with the Protocol Section 5.2. Added "at investigator discretion Follicle Stimulating Hormone may be retested after the Screening visit."

Rationale: *To align with language in Protocol Section 5.2 Contraception Recommendations which outlines requirements for females to be considered of non-childbearing potential. To align with addition of language in Protocol Section 5.2 which permits re-testing of FSH during study conduct.*

- Operations Manual, Section 3.16 Clinical Laboratory Tests, Pregnancy Tests (Serum and Urine): Added language to clarify requirements for serum and urine pregnancy testing during the study and add home urine pregnancy testing at a minimum of monthly intervals.

Rationale: *To clarify requirements for serum and urine pregnancy testing during the study and add home urine pregnancy testing at a minimum of monthly intervals. Greater than monthly intervals between on-site visits in LTE Period 2 occur; thus, specific timepoints for serum and urine pregnancy testing are found in the Activity Schedule (Appendix E) and Operations Manual Section 2.1 Individual Treatment Period Visits Activities.*

- Operations Manual, Section 3.16 Clinical Laboratory Tests, Hepatitis Screening: Added language to Figure 1 to inform that HBV DNA PCR may be tested at unscheduled visits, if necessary.

Rationale: *To provide instruction for subjects requiring HBV DNA PCR testing every 12 weeks to have an unscheduled visit to test HVB DNA PCR when planned visits are not at 12-week intervals.*

- Operations Manual, Section 3.16 Clinical Laboratory Tests, Tuberculosis Prophylaxis: Deleted duplicate "at least" and underscore between "rifampin must."

Rationale: *To correct typographical errors.*

- Operations Manual, Section 3.16 Clinical Laboratory Tests, Hypersensitivity Testing: Simplified instructions for sample collection.

Rationale: *To clarify that the laboratory manual provides all the instructions necessary for sample collection.*

- Operations Manual, Section 3.19 Home Healthcare Services after Week 24: Corrected spelling of healthcare.
Rationale: *To correct the typographical error.*
- Operations Manual, Section 5.2 Treatment After End of Study: Updated last study visit to Week 182.
Rationale: *To reflect the updated study design with the LTE Period 2.*
- Operations Manual, Section 6.1, Treatments Administered: Updated section to add paragraph detailing training requirements for subjects or designees on home administration of study drug and instructions for study drug administration for LTE Period 2.
Rationale: *To provide guidance for training of subjects or designees on home administration of study drug and on-site and at home study drug administration for the LTE Period 2.*
- Operations Manual, Section 6.2, Packaging and Labeling: Removed statement that each syringe and carton will be labeled as required per country requirements.
Rationale: *To remove redundant information.*
- Operations Manual, Section 6.4, Selection and Timing of Dose for Each Subject: Added instruction for handling of dosing of ABBV-154/placebo outside of the visit window.
Rationale: *To provide guidance for minimal timing between doses in case of unanticipated out of window dosing to ensure subject safety.*

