 - ✓ 26. Subject must not have been treated with **any investigational drug** within 30 days or 5 half-lives of the drug (whichever is longer) prior to the first dose of study drug or is currently enrolled in another interventional clinical study or was previously enrolled in this study.
 - ✓ 27. Subject must not have received **any live vaccine** within 4 weeks (or longer if required locally) prior to the first dose of study drug or have expected need of live vaccination during study participation including at least 70 days after the last dose of study drug.
 - ✓ 28. Subject must have discontinued all opioid and analgesic medications, with the exception of non-steroidal anti-inflammatory drugs (NSAIDs), acetaminophen, tramadol, combination of acetaminophen with codeine, or combination of acetaminophen with hydrocodone. Subjects entering on analgesics must be on stable dose ≥ 1 week prior to the first dose of study drug.
 - ✓ 29. Subjects must not have been treated with oral traditional Chinese medicine within 4 weeks prior to the first dose of study drug.

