5.3 Prohibited Medications and Therapy

In addition to the medications listed in the eligibility criteria, prior exposure to ABBV-154 or ABBV-3373 are NOT allowed. The following medications are prohibited through the end of study drug administration:

- All csDMARDs, except MTX;
- All tsDMARDs: Examples include but are not limited to the following: Xeljanz[®] (tofacitinib), Olumiant[®] (baricitinib), Rinvoq[®] (upadacitinib), Jyseleca[®] (filgotinib);
- All bDMARDs, including bio-originators and biosimilars. Examples include but are not limited to the following: Humira[®] (adalimumab), Enbrel[®] (etanercept), Remicade[®] (infliximab), Kineret[®] (anakinra), Rituxan[®] (rituximab), Cimzia[®] (certolizumab pegol), Simponi[®] (golimumab), Actemra[®] (tocilizumab), Raptiva[®] (efalizumab), Tysabri[®] (natalizumab), Stelara[®] (ustekinumab), Benlysta[®] (belimumab), Orencia[®] (abatacept);
- Through Week 24, oral glucocorticoids with the exception of prednisone ≤ 7.5 mg/d (or equivalent) at Baseline, which must be tapered to 0 within 4 weeks of Baseline unless a subject qualifies for rescue therapy as defined in Section 5.4;
- Any intra-articular, intramuscular, parenteral, trigger point or tender point, intra-bursa, or intra-tendon sheath glucocorticoid through Week 24 unless a subject qualified for rescue therapy defined in Section 5.4;
- Super high potency and high potency topical glucocorticoids;
- Any investigational drugs;
- Any live vaccination;
- Any opioid medications with exception of tramadol, combination of acetaminophen with codeine, or combination of acetaminophen with hydrocodone; and
- Any oral traditional Chinese medicine (e.g., tripterygium glycosides, sinomenine, total glucosides of white peony).

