Subjects must be able to safely discontinue any prohibited medications as specified in Section 5.1. Subjects must consent to the study prior to discontinuing any prohibited medications for the purpose of meeting study eligibility. Information regarding potential drug interactions with ABBV-154 can be located in the ABBV-154 Investigator's Brochure.

Vaccines

If the subject and investigator choose to receive/administer live vaccines, these vaccinations must be completed (as per local label) at least 28 days (or longer, if required locally) before first dose of study drug. Live vaccinations are prohibited during study participation including at least 70 days after the last dose of study drug. Examples of live vaccines include, but are not limited to, the following:

- Monovalent live influenza A (H1N1) (intranasal);
- Seasonal trivalent live influenza (intranasal);
- Zostavax (herpes zoster, live attenuated);
- Rotavirus;
- Varicella (chicken pox);
- Measles-mumps-rubella or measles-mumps-rubella-varicella;

- Oral polio vaccine;
- Smallpox;
- Yellow fever;
- Bacille Calmette-Guérin;
- Typhoid (oral).

If the live herpes zoster vaccine is to be administered and there is no known history of primary varicella (chicken pox), preexisting immunity to varicella should be confirmed with antibody testing at or prior to Screening and prior to administration of the herpes zoster vaccine. If screening varicella antibody testing is negative, the live herpes zoster vaccine should not be administered.

Administration of inactivated (non-live) vaccines is permitted prior to or during the study according to local practice guidelines. Examples of common vaccines that are inactivated, toxoid or biosynthetic include, but are not limited to, injectable influenza vaccine, pneumococcal, Shingrix (zoster vaccine, recombinant, adjuvanted), and pertussis (Tdap) vaccines.

COVID-19 Pandemic -Related Vaccination Guidance

Given the ongoing COVID-19 pandemic, selected non-live vaccines (e.g., mRNA, non-replicating viral vector, protein subunit, etc.) to prevent SARS-CoV-2 infection may be administered during screening or the treatment period, as long as components of the vaccine are not contraindicated.

The decision to receive a locally available vaccine should be based on local guidance and an individual discussion between the treating physician and the subject.

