Rationale: *The duration of contraception, pregnancy, and egg/sperm donation requirements after last dose of study drug was changed for the UK to align with local health authority request. The duration for each remains 70 days after the last dose of study drug administration globally, which represents greater than 5 times the upper limit of the mean elimination half-life, using the most conservative estimate of the half-life among the 3 analytes (ADC, total antibody, and payload) measured in circulation following subcutaneous administration of ABBV-154. Thus, at 70 days, no relevant systemic exposure to ABBV-154 is expected to be present.*

- Protocol Section 5.1, Eligibility Criteria: Updated criterion #24 to add "interventional" to describe clinical study type.

Rationale: *To specify that subjects cannot be enrolled in another interventional study. Noninterventional studies are permitted, as they are not expected to impact safety or efficacy of this study.*

- Protocol Section 5.1, Eligibility Criteria: For criterion #25, corrected a typographical error in the period of time to refrain from live vaccination after last dose of study drug from 12 weeks to 70 days and add clarification that 4 weeks is the minimum amount of time between receipt of a live vaccine, but duration may be longer if required locally.

Rationale: *To align with Protocol Section 5.4 and to ensure that a live vaccination is not administered during periods of relevant systemic ABBV-154 exposure, as 70 days is greater than 5 times the upper limit of the mean elimination half-life of subcutaneously administered ABBV-154.*

- Protocol Section 5.2, Contraception Recommendations: Corrected requirement #1 for Females, Non-Childbearing Potential to "Premenopausal" from "Postmenopausal." Corrected the follicle-stimulating hormone level to ≥ 30 IU/L from > 30 IU/L.

Rationale: *To correct the typographical errors.*

- Protocol Section 5.2, Contraception Recommendations: updated that both male and female condoms may be used where required by local practices in addition to the highly effective methods of birth control.

Rationale: *To clarify that where required by local practices, both male and female condoms may be used in addition to the highly effective methods of birth control which are required for all*

Females, of Childbearing Potential as either will adequately prevent the occurrence of pregnancy.

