- Protocol Section 5.2, Contraception Recommendations: Added language to allow re-testing with follicle-stimulating hormone after screening visit for female subjects that may change status from childbearing potential to non-childbearing potential during the course of the study.

Rationale: *During the course of the study, females initially classified as of childbearing potential may become postmenopausal or permanently sterile and therefore not at risk to become pregnant. For subjects not at risk for pregnancy, discontinuation of required contraception and pregnancy testing is appropriate.*

- Protocol Section 5.3, Prohibited Medications and Therapy: Changed the time period during which the list of prohibited medications is prohibited from "throughout the duration of the study" to "through the end of study drug administration."

Rationale: *To clarify that subjects may receive these medications after discontinuation of study drug.*

- Protocol Section 5.3; Prohibited Medications and Therapy: Corrected "sheet" to "sheath."

Rationale: *To correct the typographical error.*

- Protocol Section 5.4, Prior and Concomitant Therapy: Deleted text describing b/tsDMARDs by mode of action and text stating all csDMARDs except for MTX must have been discontinued.

Rationale: *As information on prior b/tsDMARD therapies which would qualify a subject for study eligibility was added to eligibility criterion #7 this information was removed from Section 5.4 to avoid duplication of information and potential for confusion. The requirement for discontinuation of all prior b/tsDMARDs and all csDMARDs, except MTX prior to the first dose of study drug was deleted to remove redundancy and potential confusion as it is included in eligibility criterion 22 and Section 5.3, Prohibited Medications and Therapy with requirements for MTX stability remaining in Section 5.4.*

- Protocol Section 5.4, Prior and Concomitant Therapy: Clarified that at Week 30 and later, subjects classified as non-responders (defined as not achieving at least 20% improvement in either TJC or SJC at both Week 24 and Week 30, or after Week 30 for at least 2 consecutive visits) will discontinue study drug and initiate standard of care therapy at the investigator discretion.

Rationale: *To improve clarity.*

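### Protocol Sections 5.3 and 5.4 give different end points for the live-vaccine prohibition: the end of dosing in one, at least 70 days after the last dose in the other

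*Protocol*

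**What the plan says.** Three places in the current protocol deal with live vaccines.

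- **Section 5.3 (Prohibited Medications and Therapy)** opens its list with "The following medications are prohibited through the end of study drug administration". One entry is "Any live vaccination". That entry has no time limit of its own and no cross-reference.
- **Section 5.4 (Prior and Concomitant Therapy, Vaccines)** states: "Live vaccinations are prohibited during study participation including at least 70 days after the last dose of study drug".
- **Section 5.1, criterion 27** excludes, among others, subjects who "have expected need of live vaccination during study participation including at least 70 days after the last dose of study drug".

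Appendix F explains two of these texts. For Section 5.3 the amendment moved the end of the window from the end of the study to the end of dosing, for the whole list. The reason given is "To clarify that subjects may receive these medications after discontinuation of study drug". For the criterion on live vaccines it set the post-dose period to 70 days, to match Section 5.4 and "to ensure that a live vaccination is not administered during periods of relevant systemic ABBV-154 exposure".

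Section 5.6 encourages subjects who stop study drug early to remain in the study and attend the regular visits.

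**The concern.** Sections 5.3 and 5.4 set different ends to the same prohibition. A site that looks up prohibited items in Section 5.3 finds live vaccines on a list whose restriction ends with dosing. The sponsor's explanation of that wording says the listed items may be taken afterwards. A site that reads the vaccine text in Section 5.4 finds a prohibition that runs at least 70 days longer.

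The stake is subject safety on the sponsor's own reasoning. Appendix F expects no relevant systemic exposure at 70 days and uses that to justify the period. The drug joins an anti-TNF antibody to a glucocorticoid receptor agonist, and Section 2.2 cites serious infection risk for TNF antagonists and for glucocorticoids.

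There is also a smaller consequence for reporting. SAP Appendix A counts subjects who took prohibited concomitant medication. Whether a live vaccine given shortly after the last dose falls in that count depends on which section is applied.

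**Working it through.** This is mainly a comparison of texts. No sample size, power or significance level is involved.

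**1. Is the conflict in current text?** Yes. Section 5.3 as it now stands carries the end-of-dosing wording, and Section 5.4 as it now stands carries the 70-day wording. Appendix F is used only to see how the sponsor reads the current wording, not as a superseded version to compare against.

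**2. Side by side.**

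| Place | What it governs | End of the restriction |
|---|---|---|
| Section 5.3 | Prohibited items during the study | End of dosing |
| Section 5.4, Vaccines | Live vaccination | Participation, including at least 70 days after last dose |
| Criterion 27 | Expected need, judged at entry | Participation, including at least 70 days after last dose |

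The gap between Sections 5.3 and 5.4 is 70 − 0 = 70 days at least.

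**3. Could the Section 5.3 list have carried a separate period?** Yes. Its entries on oral and injected glucocorticoids have their own Week 24 limit and refer to Section 5.4 for rescue therapy. The live-vaccine entry has neither a limit nor a reference.

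**4. How much drug might be present in the gap?** No half-life is stated, so the 70 days cannot be reproduced independently. SAP Section 10.2.1 equates 70 days with 5 half-lives, which gives 70 / 5 = 14 days. Appendix F says 70 days exceeds 5 times the upper limit of the mean half-life, taking the most conservative of the three analytes. So 14 days is an upper bound on that half-life. Assuming simple exponential decline from the last-dose level, the fraction remaining is 0.5^(t / half-life). The 7-day column is an assumed value, half the bound, to show the range.

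| Days after last dose | Half-life 14 days | Half-life 7 days (assumed) |
|---|---|---|
| 14 | 0.5^1 = 50% | 0.5^2 = 25% |
| 28 | 0.5^2 = 25% | 0.5^4 = 6.25% |
| 42 | 0.5^3 = 12.5% | 0.5^6 = 1.6% |
| 56 | 0.5^4 = 6.25% | 0.5^8 = 0.4% |
| 70 | 0.5^5 = 3.1% | 0.5^10 = 0.1% |

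The sum ignores continuing absorption from the injection site, so it indicates scale and is not a prediction.

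**5. What does Section 5.4 mean for a subject off drug but still in the study?** For a completer the question hardly arises. The last dose is at Week 180, 70 days is 10 weeks, and 180 + 10 = Week 190, which is when the 70-day Follow-up Visit falls. For a subject who stops under the Week 30 non-response rule, the two parts of the sentence separate. If the last dose was at Week 28, 70 days ends at Week 38. If a dose was given at Week 30, it ends at Week 40. Participation may run to Week 182, which is (182 − 30) × 7 = 1,064 days after Week 30. The text does not say whether the prohibition continues over that time.

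**The case against.** The strongest reply is that the two sections can both be obeyed. The body of Section 5.3 says what is prohibited up to the end of dosing and is silent on what follows. A site that follows Section 5.4 therefore breaches neither section. Section 5.4 has its own vaccine subsection, names examples and gives an explicit post-dose period. Criterion 27 uses the same period, and the amendment log says the two were deliberately aligned. On this view a general list is merely less complete than a specific rule.

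Much of this stands, and it rules out several stronger readings.

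- A reader might infer that Section 5.3 gives written permission to vaccinate after the last dose. It does not. It ends a prohibition, and the permissive wording is only in the Appendix F rationale.
- A reader might count three rival end points. The documents support two: the end of dosing, and one Section 5.4 sentence whose reach is unclear for subjects who stay in follow-up.
- A reader might take criterion 27 as a second operative prohibition. It is an entry criterion about expected need, so the working conflict is Section 5.3 against Section 5.4.
- A reader might conclude that every subject who stops study drug is affected. Only those for whom a live vaccine arises after the last dose are, and criterion 27 already screens out expected need.

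The reply does not remove the inconsistency. The protocol text available states no rule that Section 5.4 takes precedence, and the live-vaccine entry does not send the reader there. The sponsor's explanation of the Section 5.3 window covers the whole list. The change may have been aimed at anti-rheumatic drugs for subjects moving to standard of care, but the text does not say so.

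**Conclusion.** The concern holds as an internal inconsistency between two current sections. They differ by at least 70 days on when the live-vaccine prohibition ends, over a period in which the sponsor's own rationale treats exposure as relevant. A site relying on Section 5.3 together with its rationale could allow what Section 5.4 prohibits. A separate, smaller ambiguity is how long Section 5.4 applies to subjects who are off drug but still attending visits.

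The number of subjects concerned is unknown and probably small. The exposure figures rest on an implied half-life of at most 14 days and on simple exponential decline; a shorter half-life leaves less drug. No endpoint, analysis or sample size changes, and the only reporting effect is on the protocol-deviation count. The Operations Manual is not among the documents reviewed, so whether it settles the point could not be checked. The point should be corrected because it concerns safety and is cheap to put right. Nothing here says which period is right.

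**What to change.** Reconcile Sections 5.3 and 5.4 so that both state the same end point for live vaccination. The wording should say explicitly what applies to subjects who have stopped study drug but remain in follow-up. Then check that criterion 27 agrees. The clinical team decides the period.

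The cost is about one sentence in a protocol amendment, with no new procedures, data or subjects.
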